9.2.1. Pharmacokinetics

A total of 22 blood samples per patient will be collected for PK purpose.

Individual plasma concentrations of ABX464, NGIcABX464, DRV, and RTV or COBI will be presented by treatment and time points. Descriptive statistics for the plasma concentrations will be presented as number of available data (N), mean, standard deviation (SD) and will be calculated if at least 2/3 of the plasma values per time-point are above LOQ (i.e. $N \ge 10$ if 15 patients are available for a given group). For descriptive statistics calculations, BLQ concentrations below the limit of quantification will be set to zero (0) if they are reported before the first quantifiable sample or considered as missing data if they are reported after the first quantifiable data.

Then, the following PK parameters will be derived for ABX464, NGIcABX464, DRV, and RTV Day 53 for each patient:

 C_{max} , t_{max} : the maximum plasma concentration (C_{max}) and the time taken to reach C_{max} (t_{max}) will be obtained directly from the concentration-time data.

AUC_{0- τ}: the area under the concentration-time curve from time zero to the time of dosing interval τ (24 h post-dose for ABX464 and NGIcABX464, and 12 h post-dose for DRV and RTV). If no concentration can be measured at this time point, AUC0-last (from time zero to the last quantifiable concentration) will be calculated. Both parameters will be presented independently. For both parameters, a linear trapezoidal method will be used.

Individual derived PK parameters will be presented by treatment and day of PK assessment when appropriate. Descriptive statistics of the PK parameters will be presented as N, mean, SD, coefficient of variation (CV %), median, minimum (Min), maximum (Max) values, and geometric mean (GM).

In the tables of individual PK parameters, all the deviations from planned analysis will be mentioned by flagging the abnormal results.

Possible exclusion of flagged PK parameters could be performed if, in the judgment of the pharmacokineticist, they are deemed not to be "pharmacokinetically relevant". Exclusion of PK parameters will be discussed in the PK results section. If data are excluded from the PK dataset, all subsequent statistical analyses will be performed twice, once using the complete available PK dataset and once using the final PK dataset as defined by the pharmacokineticist. Study conclusion will be based on the final dataset as defined by the pharmacokineticist.

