For each compound, plasma concentration vs. time curves will be presented on a log-linear scale:

- mean plots showing the data of both treatments (administration alone and co-administration with ABX464);
- by patient plots with the treatments on separate plots (spaghetti plots).

Formal PK Statistics

It is assumed that all PK data of DRV and RTV/COBI obtained with co-administration of placebo will be gathered in a placebo group accounting for a theoretical total of a minimum of 7 patients.

Evaluation of drug-drug interaction

The relative bioavailability (F_{rel}) after multiple dose administration with either co-administration of ABX464 or of placebo will be evaluated on PK parameters determined on Day 25.

The comparison will be performed on Cmax and AUC_{0-t} using a 1-way ANOVA model with treatment as main effect on logarithmically transformed data. For each parameter, a point estimate for the ratio of geometric means (DRV/RTV or COBI with 50 mg ABX464 / DRV/RTV-COBI with placebo) will be obtained by calculating the difference of least square means on the logarithmic scale and subsequent back transformation with the exponential function. Likewise, 90% confidence interval for the ratios will be obtained by back transforming the 90% confidence intervals of least square mean differences on log-transformed PK parameters.

Moreover, evaluation of steady-state will be made by visual inspection of the pre-dose concentration measurement collected over the study duration.

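### Section 9.2.1 rests the PK conclusion on the dataset left after judgement-based exclusions, although the complete-data analysis is also run

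*Protocol*

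**What the plan says.** Protocol section 9.2.1 sets out a sequence.

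- Cmax and AUC over the dosing interval are derived for each patient. On presentation it says: "Individual derived PK parameters will be presented by treatment and day of PK assessment when appropriate".
- In the individual tables, "all the deviations from planned analysis will be mentioned by flagging the abnormal results".
- The pharmacokineticist may then remove flagged values that, in his or her own view, lack pharmacokinetic relevance. The section does not define that term.
- "Exclusion of PK parameters will be discussed in the PK results section".
- If anything is excluded, "all subsequent statistical analyses will be performed twice, once using the complete available PK dataset"; the second run takes the reduced one.
- "Study conclusion will be based on the final dataset as defined by the pharmacokineticist".

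Under the Formal PK Statistics heading of the same section, the drug-interaction comparison is a one-way ANOVA on log-transformed Cmax and AUC. It yields a ratio of geometric means (with ABX464 over with placebo) and a 90% confidence interval. The placebo data are "gathered in a placebo group accounting for a theoretical total of a minimum of 7 patients". Section 9.4 gives 21 ABX464 and 7 placebo patients at a dose level.

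**The concern.** The protocol plans two versions of the interaction analysis and decides in advance which one counts: the version from which values have been removed by judgement. Candidates for removal are values already derived and flagged as abnormal, so the choice can depend on the results themselves.

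The protocol states no safeguard on timing or blinding. Individual parameters are tabulated by treatment (9.2.1). Samples for assay of ABX464 and its metabolite, as well as darunavir and the boosters, are taken from all patients (5.3.7). Section 6.5 lists who is blinded without naming the pharmacokineticist. The blind-review meeting in 9.1.1 is assigned protocol deviations only.

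At stake is the effect of ABX464 on darunavir and booster exposure, which 5.3.7 calls the main objective of the PK analysis. The reference group may be as small as seven patients, so one exclusion there has leverage. Removing an extreme value also tends to reduce the residual variance, so the interval can look more precise than the full data warrant.

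**Working it through.** The protocol states no PK sample-size calculation, CV, power or acceptance limit, so there is no figure of its own to reproduce. The check is how far one exclusion moves the planned estimate.

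**Inputs**
- 21 ABX464 patients (9.4) and 7 placebo patients (9.4, and the minimum in 9.2.1).
- Log-scale comparison with a 90% confidence interval (9.2.1).
- Between-patient CV of 30%, 40% or 50%, which is an assumption. On the log scale SD = sqrt(ln(1 + CV²)) = 0.294, 0.385, 0.472.

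**Interval width, full data**
- Log half-width = t(0.95, 26 df) × SD × sqrt(1/21 + 1/7) = 1.706 × 0.436 × SD = 0.744 × SD.
- As a multiplying factor on the ratio: 1.24, 1.33, 1.42.

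**Dropping one extreme value**
- Removing the largest of n values lowers the group's log mean, on average, by E(max) × SD / (n − 1), where E(max) is the expected largest of n standard normal values.
- Placebo, n = 7: 1.352/6 = 0.225 × SD. The ratio is multiplied by 1.07, 1.09, 1.11.
- Dropping the lowest placebo value instead multiplies it by 0.94, 0.92, 0.90.
- ABX464, n = 21: 1.889/20 = 0.094 × SD. Dropping the highest multiplies the ratio by 0.97, 0.96, 0.96.

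A simulation of 100,000 trials per CV gave the same factors.

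**Relative to the interval**
- 0.225/0.744 = 0.30. The SD cancels, so this share does not depend on the assumed CV.

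**If the dose is escalated**
- 8 + 28 patients at 3:1 give 2 + 7 = 9 placebo patients if pooled.
- Shift = 1.485/8 = 0.186 × SD, so the ratio is multiplied by 1.06, 1.07, 1.09.
- Log half-width for 21 against 9 = 1.701 × sqrt(1/21 + 1/9) × SD = 0.678 × SD. The share is 0.186/0.678 = 0.27.

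**The case against.** The strongest reply is that 9.2.1 is more guarded than it first appears. Only flagged parameters can be excluded, and flags are tied to deviations from the planned analysis. Being the highest value is not a stated ground for removal, so the calculation above shows leverage and does not predict conduct. Exclusions must be discussed and both analyses are run, so a reader of the report could see any shift. All of this stands. It limits concealment, but it does not change which result carries the conclusion.

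A second reply is that section 9 leaves technical detail to the SAP, where the meaning of pharmacokinetically relevant and the timing of exclusions may be defined. That also stands, and those gaps alone would be no finding. The choice of dataset for the conclusion is different, because the protocol itself fixes it.

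Three stronger readings are tempting but not supported.

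- **That exclusions are made unblinded.** By-treatment tables and the ABX464 and metabolite assays make this plausible. But no section says that the pharmacokineticist is unblinded or when exclusions are decided. The protocol supports only the absence of a stated safeguard.
- **That the complete dataset is unbiased.** A value from a missed dose or a mistimed sample does not measure steady-state exposure, and keeping it can also distort the ratio.
- **That the rule can flip a pass/fail result.** Section 9.2.1 plans an estimate and an interval, with no limits to pass. If limits of 0.80–1.25 are assumed, with a true ratio of 1.25 and one extreme value dropped at will, simulation raises the share of trials inside the limits from 5% to 13% at CV 20% and from 2% to 8% at CV 30%. Those limits are not in the protocol, so the conclusion here does not rely on these figures.

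**Conclusion.** The point holds as a fault in a stated rule. Section 9.2.1 assigns the PK conclusion to the judgement-reduced dataset in preference to the complete-data analysis it also produces, without requiring exclusions to be fixed before treatment or the ratio is known.

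Under an assumed CV of 30–50%, removing one extreme placebo value moves the ratio by about 7–11% with 7 placebo patients and about 6–9% with 9. That is 0.30 and 0.27 of the log half-width of the 90% interval, so a single exclusion shifts the estimate noticeably but by well under the interval's half-width.

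Severity is moderate. PK is one of several secondary objectives (2.2), the primary safety objective (2.1) is untouched, and no acceptance limit depends on the result.

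**What to change.** Amend 9.2.1 as follows.

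1. The PK conclusion rests on all available PK parameters except those with a documented dosing, sampling or assay error of a type listed in advance (for example a missed dose, a wrong sampling time or an assay failure).
2. These exclusions are decided and signed before treatment codes or ratios are seen. The darunavir, ritonavir and cobicistat data are reviewed apart from the ABX464 and metabolite results, because the latter could reveal the arm.
3. Any further judgement-based exclusion is reported only as a sensitivity analysis, with the discussion that 9.2.1 already requires.

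The cost is a few sentences and a separate data listing for the review. No extra patients or samples are needed, and analyses with and without exclusions are already planned. The downside is that a true artefact with no documentation stays in the main analysis and may widen the interval slightly.

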Since ABX464 undergoes a high level of biotransformation, ratios between metabolite and parent drug appear to be unchanged across the studied dose range but inter-individual variability prevented from definite conclusions.

Therefore, ABX464 should rather be considered as a pro-drug with regard to its short t1/2. Its metabolite, ABX464NGIc exhibits markedly higher blood concentrations and has a much longer t1/2 which could be of pharmacological interest. Last, dose-exposure relationship appears erratic between 50 and 200 mg but tends to linearity up to 150 mg.

PK Study Design

The main objective of the PK analysis is to evaluate the impact of concomitant administration of ABX464 on DRV and RTV/COBI PK characteristics.

Considering that DRV/RTV or DRV/COBI is a chronic treatment, it is deemed more relevant to evaluate the possible drug-drug interaction at steady-state.

With regard to the relatively short $t_{1/2}$ of DRV (15 h), steady-state is expected to be reached between the 3rd and the 4th day of administration. RTV and COBI have a lower $t_{1/2}$ and thus will not require a longer treatment duration to be at steady-state.

ABX464 was shown to have a very short $t_{1/2}$ (1 to 2 h), so steady-state is virtually reached at the second administration, while NGIcABX464 has a $t_{1/2}$ of 90 to 110 h, meaning that steady-state is reached after 19 to 22 days of administration. Therefore, PK blood collection is planned to be done on Day 25 (25 days after initiation of ABX464 administration). Collection of sparse pre-dose samples from Day 1 o Day 25 will allow to control that NGIcABX464 is at steady-state at the time of PK assessment and to check if steady-state pre-dose levels of DRV and RTV are maintained with co-administration of ABX464.

Since PK analysis is done at steady-state, PK blood sampling will be limited to the higher dosing interval and expression of the extent of exposure of each compound will be determined by AUC_{0-τ} (with τ =24 h for ABX464 and NGIcABX464 and 12 h for DRV and RTV).

A first blood sample (reference) for DRV and RTV/COBI will be collected on the first day of treatment before any drug administration then blood samples will be collected for PK purpose at the following days:

- Day 0 pre DRV/RTV-COBI morning dose*;
- Day 7 pre DRV/ RTV-COBI morning dose;
- Day 14 pre DRV/ RTV-COBI morning dose;
- Day 21 pre DRV/ RTV-COBI morning dose;

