11.4. Randomization

Randomization will be centrally managed by block of 4 patients (3 ABX464/1 placebo). It will be performed via the eCRF. The bottle numbers to be used for a specific patient will assign according to a pre-defined randomization list by SODIA. This information will be provided to the site by fax.

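### The formal drug-interaction model in section 9.2.1 has treatment as its only term, so it gives up precision that the booster and the Day 0 reference sample, both already collected, could provide

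*Protocol*

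**What the plan says.** Section 9.2.1, under Formal PK Statistics, fixes the comparison. Relative bioavailability "will be evaluated on PK parameters determined on Day 25", for Cmax and AUC, "using a 1-way ANOVA model with treatment as main effect on logarithmically transformed data". The ratio of geometric means is labelled "DRV/RTV or COBI with 50 mg ABX464 / DRV/RTV-COBI with placebo" and carries a 90% confidence interval. The text assumes that "all PK data of DRV and RTV/COBI obtained with co-administration of placebo will be gathered in a placebo group", with a "theoretical total of a minimum of 7 patients". The model has no booster term and no baseline term.

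Section 6.9.1 admits patients on darunavir 800 mg with either ritonavir 100 mg or cobicistat 150 mg. Section 11.4 says "Randomization will be centrally managed by block of 4 patients (3 ABX464/1 placebo"); neither it nor section 6.4 mentions stratification by booster.

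Section 5.3.7 plans this: "A first blood sample (reference) for DRV and RTV/COBI will be collected on the first day of treatment before any drug administration". Its sampling list marks Day 0 as the reference for DRV and RTV-COBI. The same section makes the effect of ABX464 on DRV and on the booster the main objective of the PK analysis. The pre-dose samples serve to check steady state and whether DRV and RTV pre-dose levels hold up under ABX464. Section 9.2.1 does this by visual inspection.

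**The concern.** Two variables known before the first dose of ABX464 may explain part of the spread in Day 25 exposure: which booster the patient takes, and the patient's own DRV level at Day 0. A treatment-only model leaves both in the residual. With 21 against 7 patients the interval is already wide, and this comparison is what the PK analysis mainly exists to deliver.

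There is also a question of meaning. RTV and COBI are different compounds given at different doses. The RTV/COBI shorthand in the Formal PK Statistics can be read as one combined booster comparison. Such a ratio would partly reflect how many COBI users fell into each arm.

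**Working it through.** **The plan's own figure.** With 3:1 allocation and 28 patients, placebo n = 28 × 1/4 = 7, which agrees with section 9.2.1. With 36 patients it is 36 × 1/4 = 9. The protocol gives no CV, correlation, booster effect or target width for the PK comparison, so those inputs below are assumptions.

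**Formula.** On the log scale the 90% half-width is h = t(0.95, df) × √[s² × (1/n₁ + 1/n₀)], with s² = ln(1 + CV²). The interval is the ratio ×/÷ exp(h).

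**Model as planned, no booster effect.** CV 40% gives s² = ln(1.16) = 0.1484. √(1/21 + 1/7) = 0.4364. With 26 df, t = 1.706. So h = 1.706 × 0.3853 × 0.4364 = 0.287 and exp(h) = 1.33, an interval of 0.75 to 1.33 around a true ratio of 1.

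**Adding log Day 0 DRV.** The residual variance becomes s²(1 − ρ²), with 25 df (t = 1.708).
- ρ = 0.5: h = 1.708 × √(0.1484 × 0.75) × 0.4364 = 0.249, factor 1.28
- ρ = 0.7: h = 1.708 × √(0.1484 × 0.51) × 0.4364 = 0.205, factor 1.23

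| CV | as planned | ρ = 0.5 | ρ = 0.7 |
|---|---|---|---|
| 30% | 1.24 | 1.21 | 1.17 |
| 40% | 1.33 | 1.28 | 1.23 |
| 50% | 1.42 | 1.36 | 1.29 |

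**Omitting booster (DRV).** If the boosters differ by a ratio r in DRV exposure and users are split 50:50, about 0.25 × (ln r)² is added to the residual variance. At CV 40%:
- r = 1.2: 0.1484 + 0.0083, factor 1.34, against 1.33 with booster in the model
- r = 1.5: 0.1484 + 0.0411, factor 1.38, against 1.33

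**Is it bias?** If 7 of 28 patients use COBI, the share of COBI users differs between arms by 25 points or more in 14% of allocations. If 14 of 28 do, it is 38%. A 25-point difference multiplies the ratio by r^0.25: 1.05 at r = 1.2 and 1.11 at r = 1.5. This varies by chance around zero on the log scale and is part of the residual spread that the interval already reflects. Simulating the treatment-only ANOVA (21 against 7, 50:50 mix, CV 40%, 100,000 trials per setting) gives 90% coverage of the true ratio, even at the extreme values r = 2 and r = 3.

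**Separate booster analyses.** With a 50:50 mix each booster has about 10–11 ABX464 and 3–4 placebo patients. At CV 40%:
- 11 against 4 (13 df): factor 1.49
- 10 against 3 (11 df): factor 1.58

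If only 7 of 28 patients use COBI, the chance that no placebo patient does is 10%.

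**The case against.** A reader might infer that the chosen model biases the result, so that booster mix could pass for an ABX464 interaction. The documents do not support that. Allocation is randomised, imbalance is chance, and coverage holds. Large distortions need booster ratios of 2 or 3, for which the protocol has no source. For DRV, section 5.3.7 describes CYP3A inhibition by COBI as roughly in line with ritonavir, which suggests a smaller ratio.

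A reader might also infer that RTV and COBI are certainly merged into one analyte. That is only one reading. Section 9.2.1 elsewhere lists RTV or COBI and plots each compound, and section 5.3.7 speaks of exposure of each compound. The ratio label may simply name the regimens compared. The wording needs clarifying, but it does not prove pooling. Nor would separate analyses be more precise; the case for them is interpretability.

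The Day 0 sample is not without purpose, since it feeds the visual check of pre-dose levels. As a single pre-dose value it cannot give a within-patient Cmax or AUC ratio, so it can serve only as a covariate.

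Finally, section 9.2 allows ANCOVA where adjustment is needed, and section 9 leaves technical detail to the SAP. That clause is generic and names no covariate, while 9.2.1 specifically fixes a one-way model. So the point is not merely a detail left to the SAP. What does stand is that the stakes are limited: PK is a secondary objective, and no equivalence bound or decision rule hangs on this ratio.

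**Conclusion.** The point holds as a loss of precision and an ambiguity of wording. The planned interval is valid but wider than necessary. The main avoidable loss is probably the unused Day 0 level: at CV 40% and a correlation of 0.5 to 0.7, the log half-width falls from 0.287 to 0.249–0.205, a reduction of 13% to 28%. A booster term for DRV adds little if the boosters act alike and a moderate amount at a ratio of 1.5. These sizes rest on an assumed CV, correlation, booster ratio and 50:50 mix. The design facts themselves are in the text.

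**What to change.** In section 9.2.1, replace the one-way model for log DRV Cmax and AUC with an ANCOVA containing treatment, booster (RTV or COBI) and the patient's log Day 0 pre-dose DRV concentration, keeping the 90% interval for the ratio. State that RTV and COBI are separate analytes, each compared between arms only among patients taking it, and that COBI is reported descriptively if too few placebo patients take it. Carry the same wording into the SAP.

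The change needs no new samples or patients. It costs up to two degrees of freedom in the DRV model (26 to 24), which is negligible here: at ρ = 0.5 and CV 40% the factor stays at 1.28. If the Day 0 level proves uninformative, almost nothing is lost. The booster-specific intervals will be wide, about ×/÷1.5–1.6 at CV 40% with a 50:50 mix, but each will refer to one compound.

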9.3. Safety Analyses

Adverse events will be coded using the standard dictionary (MedDRA) down to the lower level term (LLT).

An overall summary table will be presented (Any adverse event, any treatment emergent adverse event (TEAE), any serious adverse event (SAE), death, any grade 3 or higher adverse events from baseline to the end of Study. This analysis will be conducted on SAF population.

Two periods will be defined for TEAE:

- Any adverse event which occurs or worsens from first dosing to Day 28;
- Any adverse event which occurs after Day 28.

Adverse events will be described by primary system organ class and preferred term. Numbers and percentage of patients, and number of occurrence of adverse event will be presented for:

- TEAE;
- Serious TEAE;
- TEAE leading to drug discontinuation;
- TEAE of grade 3 or 4;
- TEAE for which relationship with the study drug is recorded as possible or probable.

The assessment of safety will be based on the frequency of adverse events (with and without regard to causality) graded according to the "Division of AIDS table for grading the severity of adult and pediatric adverse events" (December 2004) and also, the review of individual values for clinical laboratory data, vital signs and ECG focusing on the detection of abnormal values and PCSAs [potentially clinically significant abnormalities (PCSAs) determined upon investigator considerations].

Adverse events will be tabulated (counts and percents) by group. All adverse events will be listed and the data will be tabulated by body system/organ class. Adverse event tabulations will include all treatment emergent adverse events, which will be further classified by severity, and relationship to treatment and dose level.

Clinical laboratory parameters, vital signs, ECG will be summarized by using descriptive statistics (n, mean, SD, SEM, median, minimum and maximum). Number of patients with at least one abnormal values will be tabulated (counts and percents) for each parameter in summary shift tables, by group and dose.

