7. PATIENT COMPLETION AND WITHDRAWAL

7.1. Patient Completion

Treatment with ABX464/Placebo shall continue until Day 28, except if a patient fulfils a premature discontinuation criterion (defined below). After ARTs interruption (Day 28), patients will be followed up twice weekly during the first three weeks and then weekly until Viral Rebound/ART resumption criteria are met. Afterwards, specific follow-up visits should be performed every 14 days after ARTs reintroduction until the viral load has returned to undetectable levels.

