8.1. Definition of an AE

Any untoward medical occurrence in a patient or clinical investigation patient administered a pharmaceutical product and which does not necessarily have to have a causal relationship with this treatment.

An AE can therefore be any unfavorable and unintended sign (including an abnormal laboratory finding), symptom, or disease (new or exacerbated) temporally associated with the use of a medicinal product, whether or not considered related to the medicinal product.

Note: The official definition also extends to AEs occurring in the placebo arm. Because of regulatory requirements, events occurring during pre-and post-treatment periods will also be designated as AEs. Therefore, reporting of such events, AEs and SAEs, will commence when the patient is enrolled into the study (date of signature of the informed consent) up until 4 weeks after the end of the treatment visits. The period after discontinuing study drug may be extended if there is a strong suspicion that the drug has not yet been eliminated.

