8.4. Time Period, and Frequency of Detecting AEs and SAEs

Clinical Study Protocol

All AEs and SAEs occurring from the time a patient consents to participate in the study until 4 weeks after he or she has completed or discontinued the investigational product must be recorded in the patient's eCRF. Importantly, SAEs will have to be reported, either by email or by Fax, to SIMBEC- ORION within 24 hours of awareness of an SAE.

SIMBEC ORION

[contact]

[contact]

Legislative guidance requires also reporting any **related** SAEs to be reported after the patient finished the study if the investigator becomes aware of them.

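### Adverse events are recorded to about 4 weeks after study drug (8.1, 8.4) but tabulated to end of study (9.3), a point that depends on time to rebound and so may differ by arm

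*Protocol*

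**What the plan says.** **Recording.** Section 8.4 requires adverse events to be recorded from consent "until 4 weeks after he or she has completed or discontinued the investigational product". Section 8.1 sets nearly the same limit, "up until 4 weeks after the end of the treatment visits", with an extension possible if the drug is thought not to have been eliminated. Section 8.4 adds that related serious events must still be reported later if the investigator learns of them.

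**Visits.** The flow chart and 5.2.6 to 5.2.8 list adverse event reporting at the weekly interruption visits, at the ART reintroduction visit and at the 14-day follow-up visits. Section 5.2.8 makes the last of those follow-up visits, when viral load is undetectable again, the End of Study visit. For a patient who does not rebound, 3.2 ends the study 3 months after interruption.

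**Analysis.** The list for the overall table in 9.3 ends with "any grade 3 or higher adverse events from baseline to the end of Study". Two treatment-emergent periods follow: "Any adverse event which occurs or worsens from first dosing to Day 28", and "Any adverse event which occurs after Day 28". The summary measure is also given: "Adverse events will be tabulated (counts and percents) by group".

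**The concern.** Three parts of one protocol give different end points for the same data. A site that follows 8.4 may stop recording 4 weeks after the last dose; a site that follows the flow chart carries on for as long as the patient attends. The statistician who follows 9.3 tabulates to the end of study. Which events exist in the database is settled during the trial, so a later analysis plan cannot fully repair this.

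The end-of-study window also has a direction. A patient who rebounds late is watched for longer, and the trial is sized on the hypothesis that ABX464 delays rebound. Under that window, the better the drug works, the more patients on it will have at least one post-treatment event, even if the true event rates are equal. Safety is the primary objective, so the main safety tables should not carry this artefact.

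The two period definitions also differ. The first counts events that occur or worsen; the second counts only events that occur. Read literally, an event that starts on treatment and worsens after Day 28 is not a second-period event.

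**Working it through.** The plan states no figure for this point. The check asks how long each arm is observed after Day 28 under each window, and what that does to a crude percentage.

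**Inputs from the protocol**
- Median time to rebound: 7 days on placebo, at least 28 days on ABX464 (9.4); 28 is used here.
- End of study without rebound: 3 months after interruption (3.2), taken as 91 days.
- End of study with rebound: rebound plus the time to re-suppression (5.2.8).
- Recording window in 8.4: 4 weeks, taken as 28 days.

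**Assumptions not in the protocol**
- Exponential times to rebound.
- Time to re-suppression *s*: 28 days, with a range of 14 to 84.
- The same adverse event rate *r* in both arms: 0.01 per day, with 0.005 and 0.02 as alternatives.

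**Observation time to the end of study**

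With h = ln 2 / median and S = exp(−91h), mean observation after Day 28 is (1 − S)/h + s(1 − S).

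- Placebo: 1/h = 7/0.6931 = 10.1 and S = 0.0001. This gives 10.1 + 28.0 = 38.1 days.
- ABX464: 1/h = 28/0.6931 = 40.4 and S = 2^(−91/28) = 0.105. This gives 40.4 × 0.895 + 28 × 0.895 = 36.1 + 25.1 = 61.2 days.

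| Window after Day 28 | Placebo, days | ABX464, days | Ratio |
|---|---|---|---|
| 4 weeks (8.4) | 28 | 28 | 1.00 |
| End of study, s = 14 | 24.1 | 48.7 | 2.02 |
| End of study, s = 28 | 38.1 | 61.2 | 1.61 |
| End of study, s = 56 | 66.1 | 86.3 | 1.31 |
| End of study, s = 84 | 94.1 | 111.3 | 1.18 |

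The overall table also includes the 28 treatment days. With s = 28 it covers 66.1 v 89.2 days, a ratio of 1.35.

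**Share of patients with at least one event after Day 28, equal true rates**

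In a common 28-day window the share is 1 − exp(−28r), which at 0.01 per day is 1 − exp(−0.28) = 24.4%.

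To the end of study it is 1 − [exp(−rs) × h/(h + r) × (1 − exp(−91(h + r))) + S × exp(−91r)]. At r = 0.01 and s = 28:

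- Placebo (h = 0.0990): 1 − [0.756 × 0.908 × 1.000 + 0.0001 × 0.403], or about 31%.
- ABX464 (h = 0.0248): 1 − [0.756 × 0.712 × 0.958 + 0.105 × 0.403], or about 44%.

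| Rate per day | 4-week window, both arms | End of study, s = 28, placebo v ABX464 |
|---|---|---|
| 0.005 | 13.1% | 17.2% v 25.8% |
| 0.01 | 24.4% | 31.4% v 44.2% |
| 0.02 | 42.9% | 52.5% v 67.2% |

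At 0.01 per day, s = 14 gives 21.0% v 36.5% and s = 56 gives 48.1% v 56.8%. The gap shrinks as re-suppression takes longer, because that time is common to all patients who rebound.

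**The case against.** The strongest reply is that 8.4 settles the matter. If recording stops 4 weeks after study drug, every patient has the same window, rebound or not, and 9.3 can tabulate only what was recorded. That is right as far as it goes: under 8.4 there is no imbalance in observation time. But 9.3 does not say so, and the flow chart tells sites to keep collecting. The sections need reconciling.

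Other limits also stand:
- The 28-day median is a planning hypothesis and a threshold for continuing development. Without a delay in rebound the bias disappears.
- On-treatment events have their own period, equal in both arms apart from early withdrawal.
- Section 9.3 states no hypothesis test for adverse events. With 7 placebo patients at a dose level, one patient is 1/7, or 14 points, about the size of the gap shown above.

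Two stronger readings are tempting. A reader might infer that follow-up ends at rebound, because 3.1.1 says the patient is then withdrawn from the study and 7.1 describes visits "then weekly until Viral Rebound/ART resumption criteria are met". Observation would then average 10.1 v 36.1 days, a ratio of 3.6. The documents do not support this: 3.1.1 and 7.1 both go on to require 14-day visits until viral load is undetectable, and 5.2.8 lists adverse event reporting at them and places End of Study at the last one.

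A reader might also fault the protocol for giving no rates per person-time. Those may be in the statistical analysis plan, which is not shown, so their absence is not a finding.

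**Conclusion.** The point holds as an inconsistency with a conditional bias. That the cut-offs in 8.1 and 8.4 differ from those in 9.3 and the visit schedule is certain from the text. So are the open-ended second period and its omission of worsening events.

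The bias arises only if the end-of-study window governs and ABX464 delays rebound. Under the planning medians, observation after Day 28 is then about 1.2 to 2.0 times as long on ABX464, for assumed re-suppression times of 84 down to 14 days. At 0.01 events per day and 28 days to re-suppression, the spurious gap is about 13 points (44.2 − 31.4). The event rate, the re-suppression time and the exponential form are assumptions, so these figures show direction and rough size only.

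The harm is confined to the post-Day-28 tables and the overall table. The whole safety comparison is not compromised.

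**What to change.** - State one adverse event cut-off, in the same words, in 8.1, 8.4, 9.3 and the flow chart.
- In 9.3, end the second treatment-emergent period and the between-arm overall table at that common cut-off, for example 4 weeks after the last dose as in 8.4.
- Define the second period as events that occur or worsen, matching the first.
- List any events recorded after the cut-off separately, including late related serious events, outside the comparative tables.

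The cost is wording only, with no added visits or patients. The downside is that late events leave the main comparative table, though they stay listed. Reliable rates for the later period would need recording to be extended beyond 8.4, so they are not part of this request.
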